Intensive Care of Elderly: What do They Wish for Themselves?

NCT05149040

Study protocol and Statistical Analysis Plan

06.06.2021 (version 3, IBM approval)

Project Description

1. Project Title

Treatment preferences of very elderly Norwegians in the event of acute life-threatening illness, and family members' ability to predict these treatment preferences: A self-administered survey.

2. Background

Very elderly patients (aged 80 years and older) are a large and steeply increasing patient population in western intensive care units (ICUs), but the overall benefit of intensive care for these patients remains controversial [1, 2]. Will ICU admission improve survival and quality of life, or will it prolong suffering and delay natural death? In case of medical uncertainty, crucial significance is attached to the patient's treatment preferences, but less than 1 in 4 very elderly ICU patients retain decision making capacity [3]. Therefore, information about the patient's likely will is frequently sought through a family conference.

Knowledge regarding the very elderly's life sustaining treatment (LST) preferences is scarce and has recently been rated as number two of top-ten research-topics by a broad panel of experts [4-6]. To our knowledge, so far no survey instrument for this purpose exists.

Research addressing the accuracy of proxy statements by family members has only shown low to moderate correlation [7, 8]. Both internal and external validity of the existing research addressing proxy accuracy is limited.

3. Study design

The overall goal of this project is to improve critically ill very elderly patients' ICU trajectories by bringing forth knowledge about their treatment preferences, their family members' ability to predict their wishes, and by directing attention to confounders of shared decision-making under uncertainty.

3.1. Research questions:

- Which preferences do very elderly people have regarding LST in the event of acute illness warranting ICU admission?
- How accurate can close family members predict the treatment preferences of a temporarily incapacitated very elderly patient with acute life-threatening illness?
- Are there factors that impact on very elderly patients' LST preferences, and on the ability of a close family member to predict these preferences?

3.2. Preregistration:

We plan to preregister the proposed study on www.ClinicalTrials.gov.

3.2. Protocol:

Choice of method: This study has an exploratory design and aims to investigate decision-making processes regarding choices where the informants can't be exposed to an experimental decision due to both the nature of the choice and seriousness of the consequences. Despite its well-acknowledged weaknesses, hypothetic scenario-based survey research emerged as a suitable approach based on a mapping review of the medical literature and on transferred knowledge derived from decision-

making research in other fields where decisional stakes are high as for example in criminology, economy, and politics [9-12].

We plan to develop and to validate a survey instrument and to conduct a self-administered survey of Norwegian residents aged 80 and older and a close family member who likely would act as a proxy in an event of acute illness.

Target population and sampling frame: Due to ethical concerns regarding exposure of very elderly patients to hypothetical treatment choices which they in real life would not be offered, we attempt to exclude patients who are not regarded potential ICU candidates in Norway owing to low physical and/or cognitive function. Furthermore, we have limited knowledge on whether very elderly people in Norway might experience a questionnaire addressing critical illness and risk of dying as a burden. We prefer therefore a sampling method where the informants have a short face-to-face encounter with one of the investigators followed by the offer to re-contact by phone or e-mail in case of emotional distress related to completing the questionnaire. For these two reasons, we abandoned the idea of a mailed survey to a random generated population-based sample and decided to study a purposive sample of potential ICU candidates aged 80 years or more.

We plan to recruit study participants by approaching all patients ≥ 80 years at the orthopedic, ophthalmologic and ear, nose and throat outpatient clinics at Haukeland University Hospital consecutively. We will exclude patients who are blind, not fluent in Norwegian, or are not able to meet for the consultation without assistance as a rough surrogate measure of markedly reduced physical and / or cognitive function. We deem the patient populations of these outpatient clinics to be least skewed towards underlying comorbidities and chronic organ impairment compared to other medical or surgical outpatient clinics. The patients will receive an information sheet about the study upon registration, and if they are interested in participating they will receive a pair of cover letters, questionnaires and stamped return envelopes; one of each for the very elderly patient him- or herself, and one for the most likely designated proxy in the event of acute critical illness. The very elderly respondents, with age < 18 years being the only exclusion criterion, identify the potential proxy respondents. The participants are asked to complete the questionnaires by themselves and without consulting each other, and to return them by mail in the provided stamped envelope. No incentives or compensation will be offered, and no reminders will be sent. Patients having several outpatient appointments during the study period will only be approached once.

We will account for age and gender of very elderly patients approached, but not enrolled, as well as age and gender of the very elderly non-respondents. Will we not be able to account for any characteristics of non-respondents among potential proxies.

Sample size: We will use a sample size of at least 400 pairs of participants. We expect a response rate of more than 50%, and we plan to continue inclusion until we have reached at least 200 elderly respondents. For more details on the sample size calculations, see the 'Analysis' section below.

Survey construction: Table 1 summarizes the structure of the questionnaires. They start with a short summary of background information regarding intensive care in general, and expected risks and benefits for very elderly patients in particular. Then the participant is asked to make a treatment choice regarding four clinical vignettes; the very elderly person is asked only about his or her own preferences, while the proxy is asked to both indicate the likely wish of the very elderly person, and his or her own preference. Three response options are provided: wishing admission to intensive care, not wishing admission to intensive care, and wishing to not engage in the decision.

	Very elderly person (potential patient)		Potential proxy	
Cover / instructions / contact information (p.1) Background information (p.2)				
	Paragraph no.	Questions	Paragraph no.	Questions
Vignettes/scenarios 1–4	1-4	4 x 3	1-4	4 x 6
Family involvement in medical decision-making	5	5	5	3
Experiences with intensive care and advanced care planning	6	5	6	6
Demographics	7	7	9	7
Health / frailty	8	5	7	5
EuroQuol		6	8	6
Comments	9	1	10	1
Re-contact permission	10	1		
Pages / questions (total)	15 / 42		18 / 53	

Table 1: questionnaire structure

The vignettes are randomly chosen among 20 hypothetical patient histories of acute life-threatening illness causing a higher degree of acute organ failure (equaling > 2 SOFA points) [13].

All vignettes are built up in a similar way, containing three paragraphs, following the same template:

1. 2–3 sentences regarding the current diagnosis and acute organ failure. The type and frequency of diagnoses is representative for ICU admission diagnosis in elderly patients in Norway and Europe (table 2). For each questionnaire, there will be four vignettes – two framed as a history of a male patient, and two framed as a female patient. The vignettes will be presented in a random order.
2. 3–4 sentences describing dichotomous therapeutic options as either intensive care with sedation requirements and some kind of invasive organ support or ward care with conservative treatment and the possibility for symptom alleviation.
3. 3 sentences on the consequences of the choice. The survival outcome estimates are based on short- and long-term outcome data from the VIP2- study data-set (table 2). The estimated quality of life regarding physical and cognitive function of ICU survivors aged ≥ 80 years is based on published data from Norway, Finland, the Netherlands and Canada [14-17], and a systematic review on cognitive impairment after intensive care [18]. Outcomes are identical for all vignettes, but in 50% of the questionnaires, the expected outcome is framed as mortality and in 50% as survival. The same framing is used for all four vignettes in each questionnaire.

ICU admission diagnosis	VIP-2 (May 2018-May 2019)					NIR (May 2018-May 2019)		
	N (%)	Survival (%)			N (%)	Survival (%)		
		ICU	30 d	6 m		ICU	30 d	1 y
Overall	3921 (100)	73	75	40	3069 (100)	86	67	47
ARF	941 (24)	75	76	34	951 (31)	84		
Sepsis	392 (14)	68	70	33	338 (11)	86		
Shock	540 (14)	72	71	34	737 (24)	88		
Acute surgery	541 (14)	80	82	45	614 (23)	86		
Trauma	233 (6)	69	70	30	215 (7)	85		
Neuro	190 (5)	68	68	30	153 (5)	87		

Table 2: Main admission diagnosis and survival of very elderly (≥ 80 år) ICU patients in Europe (VIP-2 data set, personal communication, [name], April 2021) and in Norway (NIR (Norwegian Intensive Care Registry), personal communication, [name], April 2021)

Furthermore, the survey covers items that may influence treatment preferences and proxy accuracy including: demographics, education, religion, previous experience with and / or communication about serious illness, comorbidity (Charlson Comorbidity Index, [19]), frailty (Clinical Frailty Scale, version 2, [20]), quality of life (EuroQol-5D-5L, registration ID: 30864, [21]) and projection (i.e. the proxy's own treatment preferences, [8]). Items were generated by a mapping review of the existing literature on elderly patients' treatment and end-of-life preferences and on proxy accuracy in general. Additional items were identified by discussions within the research group.

The questionnaires ask for the following free-text comments:

- Elaborating the treatment choice made after each scenario
- Expectations regarding family members contribution into the decisional process
- General comments

In order to allow for a longitudinal follow-up survey aiming at assessing very elderly's treatment preferences and proxy accuracy stability over time, the respondents are asked to provide their name and address at the end of the questionnaire. The respondents are informed that providing name and address for follow-up is voluntary, about their right to withdraw at any time and that taking part in a longitudinal cohort will impact on data handling, i.e. data will be stored pseudonymously instead of anonymously.

The longitudinal follow-up will be a separate study with revised questionnaires and revised protocol according to the findings of the cross-sectional study. New ethical approval for the longitudinal follow-up will be sought.

The layout of the questionnaire was created in compliance with the guidelines for visual design of paper questionnaires by Statistics Norway [22].

Face / Content validity: The draft of the questionnaire has been evaluated by 9 health care professionals (4 senior ICU consultants, 2 junior anesthetists, 2 ICU nurse specialists, 1 research nurse, 2 geriatricians, 1 public health specialist) and 6 laymen (2 elderly, 4 possible proxy decision makers, of those 2 with higher education, but no health care professionals).

Pre-testing: (February/March 2020): We pre-tested a preliminary version of the questionnaire containing only one vignette and no questions regarding demographic or health-related information among 20 grandparent/parent pairs of medical students. Completed questionnaires were returned anonymously by mail. The response rate was 45% with 8 complete pairs and may have been adversely affected by the coincidental society lock-down due to the CoVID-19 outbreak.

We assessed whether the case vignette was feasible, and produced responses with sufficient data dispersion to assess proxy accuracy and factors that might impact on the choices made.

Elderly's preference	N	Son's / daughter's prediction			
		Wants ICU admission	Does not want ICU admission	Wants the doctor to decide	Unsure about the elderly's preference
Wants ICU admission	3	1	1	1	
Does not want ICU admission	1		1		
The doctor should decide	4	1		2	1
Unsure	0				

Table 3: Pre-test results (cases of apparent assumed similarity in red)

We reduced and adjusted the “uncertain” and “the doctor should decide” answer categories to “wishing to not engage in the decision” after the pre-test in order to more precisely match the Norwegian regulations, where patient preferences are an important information into the medical decision process, but the ultimate decisional authority remains with the treating physician(s). Additional space for free-text comments is provided, and the respondents are asked to elaborate the reason for their preference. Moreover, we abstracted confidence into the choices made as an independent item and ask the participant to indicate for each scenario how certain they feel about their answer regarding treatment preference on a five-point Likert scale.

The pretest also revealed cases of assumed similarity, where the son/daughter apparently decided according to his/her own preferences which were different from the preferences of their elderly mother / father (red numbers in table 2). None of the respondents commented on unpleasant feelings when confronted with a question regarding life-threatening illness, but several both elderly persons and their adult children volunteered that they perceived the question to be relevant, important, and not sufficiently addressed yet.

An interesting observation from the pre-test was that respondents who opted for their physician to decide had less or no free text comments, compared to respondents who made a clear choice.

Pilot testing: We plan to assess the penultimate versions of the questionnaires (one for the very elderly person, and one for the potential proxy) for face validity, and clinical sensibility as well as to pilot them regarding relevance, flow, arrangement and time to complete.

To estimate the participants’ preferences regarding life-sustaining treatment, we will calculate the proportion of responses in each category (‘wants ICU admission’, ‘does not want ICU admission’, ‘does not want to engage in the decision’), along with 95% confidence intervals. With responses from 200 patients, we can estimate the preference proportions with an absolute margin of error less than 7%, based on 95% confidence intervals, which we deem sufficient. For example, if 50% of the respondents wanted ICU admission, the corresponding 95% confidence interval would be approx. 43%–57%.

To investigate factors associated with the participants’ LST preference, we will use (mixed-effects) logistic regression analysis. The response variables will be a) having a preference (‘wants ICU admission’ or ‘does not want ICU admission’), b) wanting ICU admission (for the subset who have a preference), or c) ‘does not want to engage in the decision’. Alternatively, we will use multinomial regression for the three preference categories. We will fit two types of models, with the following explanatory variables.

Model 1 (experimental variables):

Gender of vignette patient (two levels), survival vs. mortality framing (two levels).

Model 2 (experimental + observed variables):

Variables from model 1, and additionally age (continuous), gender (two levels), religion (three levels), comorbidity (continuous; Charlson Comorbidity Index), frailty score (continuous; Clinical Frailty

Scale), health-related quality of life (continuous; EQ-5D VAS), and experience with intensive care (two levels).

We will only have statistical power to detect large effects. For example, the effect of a binary predictor with a prevalence of 50% (e.g., the survival vs. mortality framing predictor) must correspond to an odds ratio of at least 2.33 (outcome 50% vs. 70%) for the power to be 80% or greater (with 200 participants). For continuous predictors, an odds ratio of 1.5 for the event rate at one standard deviation above the mean compared to the event rate at the mean, will be sufficient.

The above calculations are based on simple logistic regression, i.e., assuming that only *one* preference (from one patient vignette) is expressed for each participant. In practice, there will be four (correlated) preferences for each participant, and we will use statistical methods that take this into account (mixed-effects logistic regression instead of logistic regression). This will increase the statistical power; i.e., we will be able to detect lower odds ratios.

To assess the proxies' ability to predict their family member's preference, we will estimate the overall percentage agreement. Again, the absolute margin of error will be less than 7% (based on a 95% confidence interval). We will also estimate the agreement stratified by the family member's preference. Other measures of agreement (e.g., chance-corrected agreement) may also be calculated.

Furthermore, we will attempt to use (mixed-effects) logistic regression to examine variables associated with 'correct prediction' (and additionally stratified by the elderly's preference [23]). Only responses where the elderly has a preference ('wants ICU admission' or 'does not want ICU admission') will be included [24]. The analysis will only be carried out if enough elderly patients have a preference (we aim to have at least 5, and preferably 10 preferences, for each predictor variable that is included). The following predictors may be included:

Proxy's prediction, elderly's and proxy's certainty in the proxy's prediction of elderly's preference, proxy's preference, proxy's experience with intensive care, communication about end of life decisions, elderly's gender, proxy's gender, interaction between elderly's and proxy's gender, absolute difference in age between the elderly and the proxy, and proxy's assessment of elderly's frailty. (Predictors with high multicollinearity may be excluded.)

In all analyses where multiple responses are included for each participant or pair, we will use statistical methods that take this into account (e.g., mixed-effects logistic regression instead of ordinary logistic regression).

If free-text comments result in rich data, they will be analyzed by Systematic Text Condensation (STC) [25] and published separately.

4. Project organization

4.1. Research group:

Principal investigator:

[name] [name], SSAI and European Diploma of Intensive Care. Senior consultant at the Department of Surgical Services, Intensive Care Unit, Haukeland University Hospital.

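### In the stratified 'correct prediction' models the proxy's prediction fixes the outcome, and in the pooled model its 'not engage' level does; the per-predictor rule counts analysed rows, not the rarer outcome

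*Combined protocol and SAP*

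**What the plan says.** All of this is in section 3.2 (Protocol), under Analysis, unless noted.

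- The planned regression has *correct prediction* as its outcome. It is fitted overall and "additionally stratified by the elderly's preference".
- The analysis set is limited: "Only responses where the elderly has a preference" enters, meaning the elderly person wants or does not want admission.
- The model is run only when a sufficient number of the elderly patients express a preference; the threshold reads: "we aim to have at least 5, and preferably 10 preferences, for each predictor variable that is included".
- The candidate list begins: "Proxy's prediction, elderly's and proxy's certainty in the proxy's prediction of elderly's preference, proxy's preference". It continues with the proxy's intensive care experience, end-of-life communication, both genders and their interaction, age difference, and frailty as the proxy rates it. Inclusion is optional. The only stated ground for leaving a predictor out is high multicollinearity.
- A simpler breakdown is also planned: "We will also estimate the agreement stratified by the family member's preference".
- Under Survey construction: "Three response options are provided: wishing admission to intensive care, not wishing admission to intensive care, and wishing to not engage in the decision". A prediction can therefore take three values.

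**The concern.** There are two separate problems.

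The first is structural. The outcome is defined by comparing the proxy's prediction with the elderly person's preference. Once the preference is held fixed by stratifying, the prediction is the outcome under another name. The multicollinearity clause does not catch this, because it concerns relations among predictors, not between a predictor and the outcome. More data does not help.

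The second concerns the threshold. A logistic model is limited by the less frequent of its two outcomes per estimated parameter. The plan counts preferences, and after the restriction of the analysis set those are simply the rows analysed. A model could meet the rule with few incorrect (or few correct) predictions behind each coefficient.

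Factors affecting a family member's ability to predict are part of the third research question (section 3.1), and this is the only regression planned on them.

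**Working it through.** **Step 1: does the prediction fix the outcome?** Score each combination (1 = correct, 0 = not correct), taking a *not engage* prediction as not correct. The plan implies that scoring but does not state it.

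| Elderly person's preference | Proxy predicts *wants* | *does not want* | *not engage* |
|---|---|---|---|
| *wants* | 1 | 0 | 0 |
| *does not want* | 0 | 1 | 0 |

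Each row is one stratified model. Within a row the outcome is constant at every level of the predictor, so separation is complete. Pooled over both rows, *wants* and *does not want* can each be right or wrong, while *not engage* is always wrong. Fits to simulated data agree:

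- the stratum model was singular;
- the pooled three-level model gave a *not engage* coefficient of −26.9 with a standard error of about 97,000;
- the pooled two-level model fitted normally (standard error 0.45).

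**Step 2: what the threshold guarantees.** The plan gives no derivation for 5 or 10, so there is no figure to reproduce. If a share q of predictions is incorrect, rarer outcomes per variable = preferences per variable × min(q, 1 − q), and min(q, 1 − q) cannot exceed 0.5. Counted in responses:

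- 5 per variable: at most 5 × 0.5 = 2.5;
- 10 per variable: at most 10 × 0.5 = 5.

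**Step 3: number of parameters.** The list has 11 terms, counting the two certainty ratings separately. Without the proxy's prediction 10 remain. Coding the proxy's own preference with three levels and every other item with one degree of freedom gives 11 parameters.

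The rule is then met from 10 × 5 = 50 preferences. Five rarer outcomes per parameter need at least 5 × 11 / 0.5 = 110. So 50–109 preferences pass the rule but cannot reach 5 at any accuracy.

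**Step 4: planned size.** From the plan: at least 200 elderly respondents and four vignettes each. Assumed: all 200 form complete pairs, 50% of responses express a preference, and 20–50% of predictions are incorrect. The plan gives no value for the last two. Responses: 200 × 4 × 0.5 = 400. Per parameter = n × q / 11.

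| Model | n | q = 20% | q = 50% |
|---|---|---|---|
| Pooled | 400 | 7.3 | 18.2 |
| Stratum, even split | 200 | 3.6 | 9.1 |
| Smaller stratum, 3:1 split | 100 | 1.8 | 4.5 |

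The stratum of 200 reaches 5 per parameter once 5 × 11 / 200 = 27.5% are incorrect. The stratum of 100 meets the preferred 10 preferences per variable (100 / 10 terms) but stays below 5 throughout this range.

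**Step 5: the documents' only counts.** In Table 3, 4 of 8 elderly people had a preference, split 3:1. Of those 4, 2 were predicted correctly (exact 95% interval 7–93%), which is too few to plan on. One of the 2 errors was a *doctor to decide* prediction. That category was later folded into *not engage*, "after the pre-test in order to more precisely match the Norwegian regulations", so the separating level did occur.

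**Step 6: how much harm at these sizes.** I simulated a random-intercept logistic model with pair standard deviation 1 and 4 vignette-level and 7 pair-level standard normal predictors. One predictor of each kind had an odds ratio of 2, the rest 1. About 32% were incorrect, with 2 or 4 answers per pair. A fit failed if any log odds ratio exceeded 8 in size or the random-intercept standard deviation exceeded 6.7.

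- 52 preferences: more than 10% of fits failed.
- 100 preferences: 2.5% or fewer failed. The central 95% of estimates for the pair-level odds ratio ran from about 1 to between 5.5 and 7.3.
- 200 preferences: practically none failed; the range was about 1.3 to 4.

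**The case against.** The strongest case for the plan is that the text is tentative throughout. The regression is to be attempted, predictors may be included, the threshold is an aim, and the design is exploratory. The threshold applies to predictors actually included, so the list can shrink, and the stratified agreement is a ready fallback. This stands and limits the severity. It does not make a listed predictor estimable where it equals the outcome.

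A reader might infer that the proxy's prediction is invalid in every model. The documents do not support that. In the pooled model, asking whether *wants* predictions are right more often than *does not want* predictions is a legitimate question with an estimable answer. The *not engage* problem also depends on scoring that response as not correct.

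A reader might also infer that the regression fails at the planned size. It does not: 50–109 preferences correspond to about 50 / (4 × 0.5) = 25 to 109 / (4 × 0.5) ≈ 55 complete pairs under the assumptions above. The target of 200 is for elderly respondents, so complete pairs may be fewer, but that would be a very large loss. The 3:1 split rests on four people.

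Two further points stand. The plan speaks of both patients and preferences. If patients are counted, each gives up to four responses, and the ceilings of 2.5 and 5 rise to as much as 10 and 20 before allowing for clustering. The threshold can also be read as applying to each fitted model; the plan does not say that it does. Finally, most 11-parameter fits at 100 preferences converged, so a rarer-outcome threshold mainly protects precision and does not mark where fitting breaks down.

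**Conclusion.** The point holds in this limited form. The proxy's prediction cannot be used in the models stratified by the elderly person's preference, and its *not engage* level cannot be estimated in the pooled model when scored as not correct. Both follow from the definitions and hold at any sample size.

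The threshold is a secondary weakness: it counts rows, leaves the unit open, and does not say that it applies to each stratum. At the assumed planned size the pooled model is probably adequate. An evenly split stratum is adequate or somewhat thin, depending on accuracy. A small stratum would give imprecise estimates more often than failed fits. These sizes rest on the assumed number of complete pairs, share with a preference, share incorrect and parameter count.

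Severity is minor to moderate: the analysis is exploratory and the repair is cheap.

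**What to change.** Change the Analysis text in two places.

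1. Omit the proxy's prediction from the stratified models. In the pooled model, use it only in a fit restricted to responses where the proxy predicted *wants* or *does not want* ICU admission.
2. Restate the threshold, for example: *at least 5, preferably 10, of the less frequent of correct and incorrect predictions per estimated regression parameter, counted in responses and checked separately for the pooled model and each stratum. If this is not met, predictors are removed in an order stated in advance; if it still is not met, only the stratified agreement is reported.* The investigators should choose the order.

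The cost is two or three sentences. The downside is fewer predictors: at 5 per parameter, a stratum of 100 supports 20 / 5 = 4 to 50 / 5 = 10 parameters at 20–50% incorrect, instead of 11. A stratified model may also not be run. The restricted fit speaks only for proxies who predicted a choice.

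### The proxy-accuracy model does not list framing or vignette-patient gender, the plan's two experimental variables, and within-pair matching of framing is not stated

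*Combined protocol and SAP*

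**What the plan says.** All references are to the combined protocol and SAP.

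- **Section 3.1, Research questions.** The third question asks about factors that act on the elderly person's preferences "and on the ability of a close family member to predict these preferences".
- **Section 3.2 Protocol, Analysis (preference models).** The heading "Model 1 (experimental variables" introduces two factors: "Gender of vignette patient (two levels), survival vs. mortality framing (two levels". Model 2 keeps both and adds observed characteristics.
- **Section 3.2 Protocol, Analysis (accuracy model).** The regression for correct prediction has its own list, opened by "The following predictors may be included". It starts with "Proxy's prediction, elderly's and proxy's certainty in the proxy's prediction of elderly's preference, proxy's preference, proxy's experience with intensive care" and goes on to communication about end-of-life decisions, both genders and their interaction, age difference and frailty. Framing and vignette gender are not on it. The model uses only responses where the elderly person states a preference.
- **Section 3.2 Protocol, Survey construction.** On framing: "in 50% of the questionnaires, the expected outcome is framed as mortality and in 50% as survival", and "The same framing is used for all four vignettes in each questionnaire". Each questionnaire has two male and two female vignettes.
- **Section 3.2 Protocol, Target population and sampling frame.** Questionnaires are handed out as a pair, one for the elderly person and one for the proxy. No section says whether the two carry the same framing, vignettes or vignette genders.

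**The concern.** The plan varies two factors by design and calls them experimental. It uses them for only half of the research question they could inform. Preference is modelled on framing and vignette gender, whereas accuracy is modelled on observed characteristics of the pair. No reason is given, and the accuracy analysis has no counterpart to Model 1. Framing may move what the elderly person answers, what the proxy predicts, or both. A reader will therefore want to know whether agreement differs by framing, and the analysis as listed will not say.

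The silence on within-pair allocation adds to this. If the two members of a pair could read different framings, some disagreement would come from the materials and would be counted as proxy error.

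**Working it through.** **1. The two predictor sets side by side**

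| | Preference models | Accuracy model |
|---|---|---|
| Framing | Models 1 and 2 | not listed |
| Vignette gender | Models 1 and 2 | not listed |
| Observed predictors | Model 2 | 11 terms |

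The 11 terms are: proxy's prediction, elderly person's certainty, proxy's certainty, proxy's preference, proxy's ICU experience, communication, elderly person's gender, proxy's gender, their interaction, age difference, and frailty. Each counts as one.

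**2. Does the plan's predictor rule explain the omission?**

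The rule is 5, preferably 10, preferences per predictor.

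- 11 terms: 11 × 5 = 55 to 11 × 10 = 110.
- 13 terms (both factors added): 65 to 130.
- 15 terms (elderly person's framing, proxy's framing, their interaction, and vignette gender added): 75 to 150.

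With 200 pairs and four vignettes, at most 800 responses are available. If half carry a preference (an assumption; 4 of 8 in the pre-test, which used other answer categories), about 400 remain. The rule does not block either factor.

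**3. The plan's own power figure**

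Inputs from the Analysis section: 200 participants, a predictor split 50:50, 50% versus 70%, power at least 80%. A two-sided alpha of 0.05 is assumed, since none is stated.

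- Odds ratio = (0.7/0.3)/(0.5/0.5) = 2.33, as stated.
- Power = Φ[(0.20 − 1.96 × √(2 × 0.6 × 0.4/n)) / √((0.25 + 0.21)/n)], with n per group.
- n = 100: (0.20 − 0.1358)/0.0678 = 0.947, power 0.828. The stated figure reproduces.

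It concerns the preference models. The plan gives no power figure for the accuracy regression.

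**4. The same contrast for accuracy**

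The recruitment target counts elderly respondents, not complete pairs, and the accuracy model drops responses without a preference. I take 100 to 200 eligible pairs as an assumed range.

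- 200 pairs, one response each: power about 83%, as above.
- 100 pairs (n = 50): (0.20 − 0.1920)/0.0959 = 0.083, power about 53%.

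Four responses per pair help. Framing is constant within a questionnaire, so the effective number of responses is (pairs × 4)/(1 + 3 × ICC). With base accuracy 50% and ICC 0.3 to 0.9 (both assumed), the odds ratio detectable with 80% power is about 1.75 to 2.2 with 200 pairs and 2.2 to 3.1 with 100.

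**5. What unmatched framing would do to agreement**

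If the two questionnaires of a pair were framed independently, 2 × 0.5 × 0.5 = 50% of pairs would be discordant. Suppose framing shifts the share wanting ICU admission by d, and the proxy knows perfectly what the relative would answer under the proxy's own framing. Agreement is then 100% in concordant pairs and at most 1 − d in discordant pairs. The overall ceiling is 0.5 × 1 + 0.5 × (1 − d) = 1 − d/2.

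| Assumed d | Overall ceiling |
|---|---|
| 5 points | 97.5% |
| 10 points | 95% |
| 20 points | 90% |

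If framing is matched within pairs, this loss is zero.

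**6. Would adding framing to the existing list be enough?**

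No. Proxy's prediction, proxy's preference and the certainty ratings are all given after the framing has been read. A framing coefficient adjusted for them is not the effect of framing on accuracy. The restriction to elderly people with a preference is a further selection that framing may affect: the plan itself models having a preference as an outcome, with framing as a predictor.

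**The case against.** The strongest reply is that little is lost. The study describes itself as exploratory, the list is permissive, and framing and vignette gender are recorded whatever the list says, so the analysis can be run later. This stands in part, and it rules out a reading that a reader might infer: that the third question loses its only randomised evidence. The preference half keeps both factors. Vignette choice and order are also random, while the plan never calls the framing split random. But the list does not present itself as a set of examples, and the plan intends preregistration. A factor added after the data are seen is not pre-specified.

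A second tempting reading is that framing is allocated by questionnaire without regard to pairs. The documents do not say that. A 50:50 split over questionnaires also results when both members of a pair receive the same version. Matching is arguably the natural reading for vignettes: with independent draws of four from 20, a pair would share only 4 × 4/20 = 0.8 vignettes on average, which would make the agreement analysis barely workable. What remains is that framing concordance is unstated.

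Third, the 90% ceiling should not be taken as an expected 10-point loss. It needs both unmatched framing and a 20-point effect. The plan gives 50% versus 70% only as a detectable size and predicts no effect.

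**Conclusion.** The point holds as an omission from the accuracy analysis. Followed as listed, the plan does not examine whether framing or vignette-patient gender affects proxy accuracy, although that is part of its third research question, both factors are recorded, and its predictor rule leaves room for them.

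The unstated matching of framing within pairs would by itself be only a missing detail. Its possible effect on overall agreement runs from zero (matched) to 2.5, 5 or 10 points (independent assignment, with assumed framing effects of 5, 10 or 20 points).

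The analysis would show only large framing effects. The 83% power assumes 200 eligible pairs with one response each and falls to about 53% with 100. Calling this an especially well-powered comparison would go too far, since any balanced binary predictor has the same power. The documents also do not support expecting a clean experimental effect from adding framing to the present list, because of the post-framing variables and the selection on having a preference.

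**What to change.** 1. Report percentage agreement by framing and by vignette-patient gender, with confidence intervals that allow for repeated responses per pair.
2. Pre-specify a first accuracy model with these two factors only, mixed-effects by pair, mirroring Model 1. Then fit the model that adds the observed predictors.
3. State that proxy's prediction, proxy's preference and the certainty ratings are measured after framing, and that the restriction to elderly people with a preference is a selection that framing may affect. Interpret the framing coefficient in the second model accordingly.
4. State that vignettes, vignette gender and framing are assigned to the pair. If framing may differ within a pair, record concordance and include it in the accuracy model.
5. Say that only large framing effects on accuracy are detectable.

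The cost is two extra model terms (more if framing may differ within pairs), a short stratified table and a sentence on allocation. No new data are needed. Item 4 has to be settled before packs are printed; section 4.3 schedules survey administration for September/October 2021. If packs have already gone out, state how they were made up and record concordance.
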